**NCT02733588**

**Document Date: February 13, 2017**

## Statistical Analysis Plan for Protocol XSGO-PB01

**Analysis Population.** Participants with a history of RYGB surgery and PBH with neuroglycopenia, uncontrolled on medical nutrition therapy and medications, were recruited from the hypoglycemia clinic. Exclusion criteria included fasting hypoglycemia, known insulinoma, major systemic illness, pregnancy, substance or alcohol abuse, recent steroid or investigational drug exposure, and use of medications (beyond hypoglycemia treatment) known to affect insulin secretion or action. The Joslin Diabetes Center Committee on Human Studies approved the study. Written informed consent was obtained from all participants. Six females and one male were enrolled. Two participants enrolled twice, in different stages of system development. All enrolled participants were included in the analysis.

**Study endpoints.** This iterative development clinical study was designed to evaluate the primary endpoints of safety and feasibility of the proposed system to predict and prevent severe hypoglycemia in patients with PBH. Secondary outcomes included prediction of imminent hypoglycemia by the automatic monitoring algorithm, minimization of time below a prespecified threshold (<75 mg/dL) using glucagon delivery, prevention of severe postprandial hypoglycemia (plasma glucose <60 mg/dL), and prevention of rebound hyperglycemia (plasma glucose >180 mg/dL) after glucagon delivery.

**Statistics.** As an algorithm iterative development study, sample size was not determined by a power calculation. Statistical analyses were performed using GraphPad Prism (GraphPad Software, La Jolla, CA). Normally distributed data were expressed as mean  $\pm$  standard deviation and skewed data were expressed as median with interquartile range. Normality was determined using the Shapiro-Wilk test. Statistical significance was determined with the Wilcoxon signed-rank test.

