Study design:	
As a first step to developing new glucagon infusion delivery strategies for hypoglycemia, development of computer algorithms to predict timing and severity of hypoglycemia onset has been initiated, in collaboration with computational scientists at Harvard University School of Engineering. We have analyzed data collected from clinically-indicated diagnostic continuous glucose monitoring systems (iPRO CGMS) obtained from patients enrolled in the hypoglycemia clinic at the Joslin Diabetes Center. Extracted data, including continuous glucose monitoring sensor glucose values, age, gender, and body mass index, and food and activity logs, were used to develop computational algorithms to allow prediction of hypoglycemia.
 
This will be a Phase 2a, single-center, open-label, proof-of-concept study designed to test the ability of the control algorithm to detect and direct timing of G-Pump™ glucagon infused from an OmniPod® pump to prevent hypoglycemia in patients with post-bariatric hypoglycemia syndrome. While the algorithm will provide an alert as to when glucagon

	should be dosed to prevent hypoglycemia, there will be no automation in this clinical trial and it will ultimately be up to the physician to initiate dosing via the OmniPod® controller.
Study location:	Joslin Diabetes Center, Boston, MA USA.
Study duration:	The total length of the study will be approximately one week per patient, and involve up to two infusions of G-Pump™ glucagon at a single visit. The total time for enrollment and treatment will be approximately 3 months.
Sample size:	For this proof-of-concept study, success will be defined as meeting the primary endpoint in 3 of 5 participants. If this is not achieved, the algorithm will be revised, and an additional 5 participants may be recruited for additional study.
Subjects:	Adult male or female patients with post-bariatric hypoglycemia syndrome
Inclusion Criteria:	
1. Males or females diagnosed with ongoing post-bariatric hypoglycemia with prior episodes of neuroglycopenia, unresponsive to dietary intervention (low glycemic index, controlled carbohydrate portions) and trial of acarbose therapy at the maximally tolerated dose.2. Age 18-65 years of age, inclusive, at screening.3. Willingness to provide informed consent and follow all study procedures, including attending all scheduled visits.

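### The SAP reads as a retrospective description under the protocol's date, so its departures from protocol v1.2 (primary endpoints, an added outcome, analysis set, test) cannot be taken as prespecified

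*SAP*

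**What the plan says.** **Dates and tense.** The SAP's title block reads "Document Date: February 13, 2017", the date that protocol v1.2 also carries. The protocol is written in the future tense: "success will be defined as meeting the primary endpoint in 3 of 5 participants", and if that fails, "an additional 5 participants may be recruited for additional study" (synopsis, Sample size). The SAP is written in the past tense. Under Analysis Population it states "Six females and one male were enrolled", "Two participants enrolled twice, in different stages of system development" and "All enrolled participants were included in the analysis". Under Statistics it states "Statistical analyses were performed using GraphPad Prism". It gives no numerical results.

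**Endpoints.** The protocol's Objectives row names one primary endpoint, validation of the controller algorithm. It lists three secondary objectives: preventing glucose below 60 mg/dL, preventing glucose above 180 mg/dL, and minutes spent in 60-180 mg/dL. The SAP's Study endpoints paragraph presents safety and feasibility as the primary endpoints the study was set up to assess. Its secondary outcomes are algorithm prediction of hypoglycemia, "minimization of time below a prespecified threshold (<75 mg/dL) using glucagon delivery", and the <60 and >180 mg/dL outcomes, both on plasma glucose.

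**Set and test.** The protocol's Biostatistical Considerations row limits the analysis set to those given at least one glucagon dose, and names repeated-measures ANOVA for the hormone profiles. The SAP analyses everyone enrolled, and its only test of significance is the Wilcoxon signed-rank test.

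**The concern.** A forward plan cannot contain a count of who enrolled, by sex, or of who came back for a second stage. Whoever wrote this text knew the enrolment and, going by its tense, was describing analyses already done. The study is open-label, so responses were visible as they accrued.

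A SAP is normally relied on to show which outcomes, populations and tests were chosen before the data could influence the choice. A reader who took the shared date at face value could accept a replaced primary endpoint, a new outcome and an unspecified significance test as part of the original design. The trial could then be judged on endpoints other than those its protocol set, while the protocol's own success criterion goes unreported.

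**Working it through.** No sample-size or power figure can be reproduced, because the SAP says there was no power calculation. The check is a comparison of the two documents, with simple counts.

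**1. Enrolment facts in the SAP.** People: 6 + 1 = 7. Two enrolled twice, so participant-enrolments: 7 + 2 = 9. The protocol foresees 5, with up to 5 more (5 + 5 = 10), and does not mention re-enrolment. The figures 7 and 9 are observed counts, not planned ones.

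**2. What the date can mean.** If 13 February 2017 is when the SAP was written, those seven people had already enrolled by then. If the date is a label taken from the protocol, the SAP was written at some other time, still after they enrolled. On either reading the text was written after enrolment.

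**3. Endpoints side by side.**

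| SAP outcome (SAP rank) | Protocol v1.2 |
|---|---|
| Safety (primary) | Planned as a descriptive summary, not as the primary endpoint |
| Feasibility (primary) | Not named as an endpoint |
| Algorithm prediction (secondary) | Nearest match to the protocol's primary endpoint |
| Time below 75 mg/dL (secondary) | Not an outcome; 75 mg/dL is the sensor alert trigger |
| Plasma glucose <60 mg/dL (secondary) | Secondary, same limit |
| Plasma glucose >180 mg/dL (secondary) | Secondary, same limit |
| Absent | Time in 60-180 mg/dL (secondary) |
| Absent | 3-of-5 success rule |

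The SAP lists 2 + 4 = 6 outcomes and the protocol 1 + 3 = 4. Two of the six keep both content and rank. One (time below 75) is new as an outcome, one (feasibility) is not named in the protocol, one (safety) is planned work with a new rank, and one (prediction) resembles the protocol's primary endpoint but is now secondary.

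**4. Glucose source.** The protocol's 75 mg/dL trigger is a sensor value (synopsis, Brief outline of treatments, Visit Day 3). The SAP specifies plasma glucose for <60 and >180 but no source for time below 75.

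**5. Analysis set.** Everyone given glucagon was enrolled, so the SAP's set contains the protocol's set. It can differ only by enrolled people who were never dosed, and neither document says how many there were.

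**6. Test.** The SAP does not say what the signed-rank test compares, or whether the unit is the person (7) or the enrolment (9). Assuming no ties or zero differences, the smallest attainable two-sided exact p-value is 2/2^n: 2/2^7 = 0.0156 for 7 pairs and 2/2^9 = 0.0039 for 9. The documents set no significance level. If 0.05 were used, a nominally significant result would be attainable with either unit, so it matters whether the test was planned.

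**The case against.** The strongest defence is that the SAP hides nothing. It gives its counts, its repeat enrolments and the lack of a power calculation openly, and few readers would mistake it for a forward plan. Revising the algorithm and adding participants were foreseen in the protocol, and protocol success was a count of participants, not a p-value. This lowers the risk of deception, but it does not explain why the stated primary endpoints differ from the protocol's or why the success rule is gone.

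The defence also rules out several stronger readings:

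- *That the 75 mg/dL threshold was not prespecified.* In the SAP the word applies to the threshold, and the protocol does specify that value as the sensor trigger. Only time below it, as an outcome, is missing.
- *That safety was added afterwards.* The Biostatistical Considerations row plans ongoing review and descriptive summary of adverse events, vital signs, examination, laboratory values, EKG and local tolerability. Only the primary rank is new.
- *That the SAP's date is false, or that it was written with results in hand.* The documents settle neither. The protocol is version 1.2, and an amended protocol can keep prospective wording after recruitment has begun. That analyses were complete rests on verb tense alone.
- *That outcomes were chosen to flatter the system.* No result is shown and no favourable selection is demonstrated. The all-enrolled set is no narrower than the protocol's.

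**Conclusion.** The concern holds in a limited form. The SAP was written after enrolment and cannot serve as evidence that its content was fixed beforehand.

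Five items found only in the SAP lack support as prespecified: the primary rank of safety, feasibility as a primary endpoint, time below 75 mg/dL as an outcome, the all-enrolled set, and the Wilcoxon test. Three protocol elements are lost or displaced: controller validation as primary, the 3-of-5 rule, and time in 60-180 mg/dL. The <60 and >180 mg/dL outcomes are unaffected.

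The effect on bias cannot be computed from the documents. The conclusion assumes that no earlier dated document supports the SAP's choices; the copy of the SAP read here lacks the text that precedes its title block. The change should be made, because it alters what the trial can claim as planned.

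**What to change.** - State when the SAP was written and whether data had been seen by then.
- Restore controller validation as the primary endpoint, reported against the 3-of-5 rule, and say which of the nine participant-enrolments counted towards it.
- Report <60 mg/dL, >180 mg/dL and minutes in 60-180 mg/dL as the protocol's secondary outcomes.
- Keep safety as a planned descriptive summary.
- Label the five SAP-only items listed in the verdict as post hoc unless an earlier dated document supports them, and report post hoc outcomes descriptively.
- Keep the word *prespecified* for the 75 mg/dL threshold, but do not apply it to time below that threshold as an outcome. State whether that outcome uses sensor or plasma glucose.

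The cost is wording in the SAP and report, plus a little extra reporting; no new data are needed. The downside is that some outcomes lose prespecified status.

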Biostatistical Considerations:	
All subjects who have received at least one dose of glucagon will be included in the data analysis set. Adverse events, vital signs, physical examination, laboratory safety variables (Screening to Final Visit), EKG (Screening to Final Visit), and local tolerability data will be reviewed and summarized on an ongoing basis during the study to evaluate the safety of subjects. Safety data will be presented in tabular and/or graphical format and summarized descriptively, where appropriate.
 
Sensor and glucagon delivery request will be collected and evaluated for specificity and response time.
 
Glucagon, insulin, and incretin plasma concentration profiles will be analyzed with commercially available analytical methods and examined using repeated-measures ANOVA.
 
Success will be defined as meeting the primary endpoint in 3 of 5 participants. If this is not achieved, the algorithm will be revised, and an additional 5 participants may be recruited for additional study.

--------------------------------	---

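### The SAP omits the protocol's 3-of-5 success rule and analyses first and repeat enrolments, at different system stages, without separating them

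*SAP*

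**What the plan says.** **Protocol, Sample size.** The criterion is stated as "success will be defined as meeting the primary endpoint in 3 of 5 participants". The next sentence gives the consequence of missing it: "If this is not achieved, the algorithm will be revised, and an additional 5 participants may be recruited for additional study". Biostatistical Considerations repeats both sentences, so the rule appears in the protocol's statistics section as well as its design section.

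**Protocol, Objectives.** The primary endpoint is validation of the controller: it must recognise when a dose is needed and time that dose as programmed.

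**Protocol, Study duration.** Participation lasts about a week and will "involve up to two infusions of G-Pump™ glucagon at a single visit". Nothing in the protocol describes a person entering twice, or being replaced.

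**Protocol, Biostatistical Considerations.** The analysis set is defined by dosing: "All subjects who have received at least one dose of glucagon will be included in the data analysis set".

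**SAP, Analysis Population.** Recruitment is reported in the past tense: "Six females and one male were enrolled. Two participants enrolled twice, in different stages of system development". All enrolled participants are analysed.

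**SAP, Study endpoints and Statistics.** The study is described as iterative development. The primary endpoints are safety and feasibility, and prediction of hypoglycemia is a secondary outcome. Sample size is said not to rest on a power calculation. The Wilcoxon signed-rank test is the only significance test named. Neither section mentions 3 of 5, a first cohort, the number of enrolments per stage, or how the two people who enrolled twice are counted.

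**The concern.** The protocol ties continuation to the primary result: the algorithm is to be revised and more people recruited if the first five fall short. Whether and why the study went on is therefore information about the primary endpoint. A SAP that reports continuation without the rule or its outcome leaves three questions open:

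- Did the controller, as first tested, meet the protocol's criterion?
- Which version of the algorithm does each observation describe?
- Is the unit of analysis a person or an enrolment?

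The first decides what the trial can claim. The second matters because a single summary across stages describes no one system. The third matters because two enrolments of the same person are not independent, and with numbers this small two extra observations change what the signed-rank test can show.

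**Working it through.** There is no power or alpha figure to reproduce, because the design is a count rule. The check is to count enrolments and compare them with the rule.

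**Step 1. Counts.** Inputs are from SAP, Analysis Population: six females, one male, two people enrolled twice.

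| Reading of the seven | People | Enrolments | Share that are repeats |
|---|---|---|---|
| People | 6 + 1 = 7 | 7 + 2 = 9 | 2/9 = 22% |
| Enrolments | 7 − 2 = 5 | 7 | 2/7 = 29% |

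The first reading is the more natural one, but the text does not settle it.

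**Step 2. Comparison with the rule.** Inputs are from Protocol, Sample size: a first cohort of 5, and up to 5 more if fewer than 3 succeed.

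- With 7 people, enrolment passed the first cohort.
- With 5 people, the number of participants fits the first cohort exactly. The two repeat enrolments, at a different stage of development, still point to a changed system.

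On either reading, two explanations remain. The first cohort missed 3 of 5 and the protocol's own path was followed, or the study continued for a reason outside the rule.

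**Step 3. How many new people met the later system?** Assume two stages, at most five enrolments in each, and each repeat person in both.

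- 7 people, 9 enrolments: the possible splits are 5 + 4 (2 new, 2 repeat) or 4 + 5 (3 new, 2 repeat).
- 5 people, 7 enrolments: 5 + 2 (0 new), 4 + 3 (1 new), 3 + 4 (2 new) or 2 + 5 (3 new).

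If the first stage was a complete cohort of five different people, only 5 + 4 and 5 + 2 remain. The later system was then tried in 7 − 5 = 2 new people, or 5 − 5 = 0. The SAP does not state the number of stages, so this is conditional.

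**Step 4. Can the first-cohort result be inferred?** With true success rate p (assumed, since the documents give none), the chance of missing 3 of 5 is P(X ≤ 2), X ~ Binomial(5, p). At p = 0.6: 0.4⁵ + 5(0.6)(0.4⁴) + 10(0.6²)(0.4³) = 0.010 + 0.077 + 0.230 = 0.32.

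| p | 0.4 | 0.5 | 0.6 | 0.7 | 0.8 | 0.9 |
|---|---|---|---|---|---|---|
| P(miss 3 of 5) | 0.68 | 0.50 | 0.32 | 0.16 | 0.06 | 0.01 |

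The range is too wide to infer what happened. The outcome has to be reported.

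**Step 5. Effect of the counting unit on the signed-rank test.** With no ties or zeros, the smallest two-sided exact p-value is 2/2ⁿ:

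- n = 5: 2/32 = 0.0625
- n = 7: 2/128 = 0.016
- n = 9: 2/512 = 0.004

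Counting people rather than enrolments moves n from 9 to 7, or from 7 to 5. In the second case the smallest attainable p rises from 0.016 to 0.0625, above a conventional 5% level (the documents state no alpha). The value 0.004 at n = 9 is available only by treating two people's repeats as independent.

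**The case against.** Much can be said for the SAP, and most of it stands.

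- **Going past five is not a breach in itself.** Failing, revising and continuing is a path the protocol provides. The wording is also permissive: five more *may* be recruited, so a second stage of fewer than five is allowed. A reader might infer a contradiction because seven or nine is neither five nor ten. The rule does not require one of those totals, and on one reading the number of people is exactly five.
- **The SAP does disclose iteration.** It calls the study iterative and mentions different stages. What it lacks is the outcome of the rule and the reason for continuing.
- **Re-enrolment is not forbidden.** The protocol is silent on it. That repeat enrolments are not additional participants is the natural reading, supported by the single-visit description, but it is a reading.
- **Undosed or non-evaluable people might explain the excess.** Dosing followed an alert, and the protocol analyses only those dosed. This is possible but weak: there is no replacement rule, the SAP analyses everyone enrolled, and it would not explain the different stages.
- **Some enrolment may have preceded protocol version 1.2.** This cannot be checked here. If it is the explanation, one sentence would settle that part.
- **Results belong in the study report, not a SAP.** Agreed. The SAP should carry the rule and the counting conventions.

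A reader might also set 3 of 4 in a second stage against 3 of 5. The protocol sets no second-stage threshold, and a denominator of four would include the repeat enrolments, so that comparison has no basis.

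**Conclusion.** The point holds as a gap in the analysis plan. As written, the SAP does not evaluate the protocol's success rule, and it separates neither algorithm versions nor first from repeat enrolments. Two of 9 enrolments (or 2 of 7) are repeats. If the first stage was five different people, the later system was tried in only 2 new people, or none.

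A reader might infer that the first cohort failed, or that the protocol was breached. The documents support neither conclusion. Both a permitted continuation and one outside the rule fit the counts, and the SAP does not let them be told apart.

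The missing rule and the missing separation do not depend on how the seven is read. The figures for new people assume two stages and a complete first cohort. The signed-rank figures assume an exact two-sided test without ties or zeros. Disclosure and a few counting rules repair the gap, so it should be fixed but does not invalidate the study.

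**What to change.** In the SAP:

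1. Restore the 3-of-5 rule, applied to the first five people in enrolment order. Use the protocol's primary endpoint (the controller detects the need and times the dose as programmed), because the SAP's safety and feasibility endpoints do not define a success for this count. Give the result in the study report.
2. Analyse and report by algorithm stage, with enrolments per stage. State why enrolment continued. If the rule was not the reason, record a protocol deviation.
3. Count each person once, at first enrolment, in any success count or signed-rank test. List the two repeat enrolments separately.
4. State whether the seven counts people or enrolments.

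The work is a short paragraph and one table. Since the SAP already reports completed enrolment, the information should be in hand. There are two real costs. A failed first cohort, if there was one, becomes visible. The analysed n also falls: with five people in a stage the signed-rank p cannot go below 0.0625, so by-stage results should be presented descriptively.
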